Investigational Drug Product

Setmelanotide (RM-493, Melanocortin-4 Receptor Agonist)

Protocol Number

RM-493-023

Protocol Title

A Phase 3 Trial of Setmelanotide (RM-493), a Melanocortin 4 Receptor (MC4R) Agonist, in Bardet-Biedl Syndrome (BBS) and Alström syndrome (AS) Patients with Moderate to Severe Obesity

Clinical Phase

Pivotal Phase 3

Treatment Indication

Treatment of obesity and hyperphagia in patients with BBS or AS

Investigator Study Sites

This study will be conducted at approximately 10 study sites located in the United States and Europe

Objective(s)

Primary

To assess the effect of setmelanotide on the proportion of patients (≥12 years of age at baseline) treated
with setmelanotide for approximately (~) 52 weeks who achieve a clinically meaningful reduction from
baseline (ie, ≥10%) in body weight.

Key Secondary

- To assess the effect of setmelanotide on the proportion of all patients who achieve a ≥10% reduction from baseline in body weight after ~52 weeks of treatment with setmelanotide.
- To assess the effect of setmelanotide on mean percent change in body weight (in patients ≥12 years of
 age at baseline) compared with baseline after ~52 weeks of treatment with setmelanotide..
- To assess the effect of setmelanotide on the proportion of patients who achieve a ≥25% improvement in the weekly average of the daily hunger score (in patients ≥12 years of age at baseline) after ~52 weeks of treatment with setmelanotide.
- To assess the effect of setmelanotide on the mean percent change from baseline in the weekly average
 of the daily hunger score (in patients ≥12 years of age at baseline) after ~52 weeks of treatment with
 setmelanotide.

Other Secondary

- To assess the effect of setmelanotide on the mean percent change from baseline in body weight (in patients ≥12 years of age at baseline) at the Week 14 visit compared with placebo.
- To assess the effect of setmelanotide on the proportion of patients who achieve a ≥25% improvement in
 the weekly average of the daily hunger score (in patients ≥12 years of age at baseline) at the Week 14
 visit compared with placebo.
- To assess the effect of setmelanotide on the mean percent change from baseline in the weekly average
 of the daily hunger score (in patients ≥12 years of age at baseline) at the Week 14 visit compared with
 placebo.

Methodology

This is a pivotal study to confirm the long-term (approximately 1 year in most patients) efficacy and safety of setmelanotide treatment in patients who have BBS or AS.

The study will consist of 3 treatment periods (see Study Schematic below). After obtaining informed consent, potential patients will be screened to determine study eligibility. Eligible patients will enter a 14-week, randomized, double-blind, placebo-controlled treatment period (Period 1) that will be followed by a 38-week open-label treatment period (Period 2) in which all patients will receive setmelanotide. The primary analysis will be performed after Period 2. To maintain the blind through Period 2, upward dose escalation to a fixed dose of 3 mg will be performed during the first 2 weeks of both the double-blind (Period 1) and 38-week open-label (Period 2) treatment periods. Following Period 2, patients will continue to receive open-label setmelanotide for 14 weeks (Period 3) after which they may be enrolled into a separate treatment extension study.

Patients will be randomized in a 1:1 ratio, stratified by age group (≥12 years or <12 years of age) and disease (BBS or AS), to receive either setmelanotide QD or placebo QD via SC injection for the first 14 weeks. Patients who are ≥16 years of age will start on setmelanotide 2 mg or matching placebo during the 2-week dose escalation and will increase to 3 mg or matching placebo at the beginning of Week 3. Patients who are <16 years of age will start on 1 mg setmelanotide or matching placebo during Week 1, will increase to 2 mg or matching placebo at the beginning of Week 2, and will increase to 3 mg or matching placebo at the beginning of Week 3. During the 14-week double-blind treatment period, patients will be evaluated at the beginning of Weeks 2 (telephone call only, patients <16 years old), 3, 7, 11, and 15 as depicted in the schematic below.

After the initial 14-week double-blind treatment period (Period 1), all patients will immediately transition to receive open-label setmelanotide QD via SC injection for 38 weeks (Period 2). To preserve the blind, all patients will be re-titrated to the 3 mg clinical dose. Thus, beginning at Week 15, patients who are ≥16 years of age will receive open-label setmelanotide 2 mg for 2 weeks, followed by a dose increase to 3 mg beginning at Week 17, and patients who are <16 years of age will receive open-label setmelanotide 1 mg during Week 15, 2 mg during Week 16, and 3 mg beginning at Week 17. Patients will be evaluated at the beginning of Weeks 16 (telephone call only, patients <16 years old) and 17 and then every 6 weeks thereafter during Period 2. In Period 3, patients will be evaluated every 7 weeks.

	2-3 Weeks				ouble-l t (Perio					Week atmen					1	14-Week Open-Labe Treatment (Period 3	
Week	Screening	1	2	3	7	11	15	16	17	23	29	35	41	47	53	59	66
		Dose 6	scalate				Dose	Escalate									
Visit	V1	V2	٧	/3	V4	V5	V6	٧	/7	V8	V9	V10	V11	V12	V13	V14	EOS
Pa	tients ≥16	2mg	/ Pbo		3mg/	/Pbo	2	mg				2				2	
Pa	tients <16	1	2mg /Pbo	1	3mg/	'Pbo	1mg	2mg				3mg				3mg	
Telephone Call				Teleph													

Study assessments will be performed at the times specified in the Schedule of Assessments (SOA). Efficacy assessments will include: body weight; BMI; hunger; body composition, including

As required in the United States (US) by the Food and Drug Administration (FDA), for clinical trials of central nervous system (CNS)-acting obesity medications,

Primary and Secondary Endpoints

The primary endpoint is:

• The proportion of patients (≥12 years of age at baseline) who achieve a ≥10% reduction from baseline in body weight (ie, are 'responders') after ~52 weeks of treatment with setmelanotide.

The key secondary endpoints are:

- The proportion of all patients, regardless of age at baseline, who achieve a ≥10% reduction from baseline in body weight (ie, are 'responders') after ~52 weeks of treatment with setmelanotide.
- Mean percent change from baseline in body weight (in patients ≥12 years of age at baseline) after ~52 weeks
 of treatment with setmelanotide.
- The proportion of patients who achieve a ≥25% improvement in the weekly average of the daily hunger score (in patients ≥12 years of age at baseline) after ~52 weeks of treatment with setmelanotide.
- Mean percent change from baseline in the weekly average of the daily hunger score (in patients ≥12 years of
 age at baseline) after ~52 weeks of treatment with setmelanotide.

Other secondary endpoints are:

- Mean percent change from baseline in body weight (in patients ≥12 years of age at baseline) at the Week 14 visit compared with placebo.
- The proportion of patients who achieve a ≥25% improvement in the weekly average of the daily hunger score (in patients ≥12 years of age at baseline) at the Week 14 visit compared with placebo.
- Mean percent change from baseline in the weekly average of the daily hunger score (in patients ≥12 years of
 age at baseline) at the Week 14 visit compared with placebo.

Number of Patients

It is anticipated that approximately 30 patients (including at least 20 with BBS and at least 6 with AS) will be enrolled and randomized across approximately 10 centers worldwide.

Inclusion Criteria

A patient must meet all of the following criteria to be eligible for this study (refer to Section 4.1 of the protocol body for potential exceptions, given the ultra-rare nature of these diseases and the associated challenges with patient identification and recruitment).

1. BBS clinical diagnosis as per Beales, 1999 (with either 4 primary features or 3 primary and 2 secondary features from table below)

Bardet-Biedl Syndrome			
Primary Diagnostic Criteria			
Rod cone dystrophy	Learning disabilities		
Polydactyly	Hypogonadism in males		
Obesity	Renal anomalies		
Secondary Diagnostic Criteria			
Speech disorder/delay	Mild spasticity (especially lower limbs)		
Strabismus/cataracts/astigmatism	Diabetes mellitus		
Brachydactyly/syndactyly	Dental crowding/hypodontia/small roots/high arched palate		
Developmental delay	Left ventricular hypertrophy/congenital heart disease		
Polyuria/polydipsia (nephrogenic diabetes insipidus)	Hepatic fibrosis		
Ataxia/poor coordination			
Source: Beales 1999			

Minor ts 6 to ≤14 years of age Obesity and/or insulin resistance and/or T2DM History of DCM/CHF Hearing loss Hepatic dysfunction	Minimum Required 2 major criteri or 1 major and 3 minor criteri
 ts 6 to ≤14 years of age Obesity and/or insulin resistance and/or T2DM History of DCM/CHF Hearing loss 	2 major criteri or 1 major and
Obesity and/or insulin resistance and/or T2DM History of DCM/CHF Hearing loss	or 1 major and
and/or T2DM • History of DCM/CHF • Hearing loss	or 1 major and
Renal failure Advanced bone age	
ents ≥15 years of age	
 Obesity and/or insulin resistance and/or T2DM History of DCM/CHF Hearing loss Hepatic dysfunction Renal failure Short stature Males: hypogonadism Females: irregular menses and/or hyperandrogenism 	2 major and 2 minor criter or 1 major and 4 minor criter
	•
	ents ≥15 years of age Obesity and/or insulin resistance and/or T2DM History of DCM/CHF Hearing loss Hepatic dysfunction Renal failure Short stature Males: hypogonadism

or AS diagnosis as per Marshall, 2007 (using major and minor age adjusted criteria in the table below).

- Note: at least 90% of patients with BBS and 100% of patients with AS must have genetically confirmed diagnosis at the time of enrollment
 - A genetically confirmed diagnosis of BBS is defined as a homozygous or compound heterozygous loss-of-function mutation in BBS genes; patients without a genetically confirmed BBS diagnosis must be reviewed with the Sponsor's medical monitor prior to enrollment.
 - A genetically confirmed diagnosis of AS is defined as a homozygous or compound heterozygous loss-of-function mutation in the ALMSI gene

Once 10% of patients without a genetically confirmed BBS diagnosis have been enrolled in the study, sites will be notified that only genetically confirmed BBS patients may be enrolled.

- 2. ≥ 6 years of age.
- 3. Obese, defined as BMI ≥30 kg/m² for patients ≥16 years of age or weight >97th percentile for age and sex on growth chart assessment for patients 6 to 15 years of age.
- Study participant and/or parent or guardian is able to communicate well with the Investigator, to understand
 and comply with the requirements of the study, and is able to understand and sign the written informed
 consent/assent.
- 5. Female participants of child-bearing potential must be confirmed non-pregnant and agree to use contraception as outlined in the protocol. Female participants of non-childbearing potential, defined as: surgically sterile (status post hysterectomy, bilateral oophorectomy, or bilateral tubal ligation), post-menopausal for at least 12 months (and confirmed with a screening follicle stimulating hormone (FSH) level in the post-menopausal lab range), or failure to have progressed to Tanner Stage V and/or failure to have achieved menarche, do not require contraception during the study.
- 6. Male participants with female partners of childbearing potential must agree to use a double barrier method contraception if they become sexually active during the study or within 90 days following their participation in the study. Male patients must also not donate sperm during and for 90 days following their participation in the study.

Exclusion Criteria

A patient who meets any of the following criteria will be excluded from this study (refer to Section 4.1 of the protocol body for potential exceptions, given the ultra-rare nature of these diseases and the associated challenges with patient identification and recruitment)

- 1. Recent intensive (within 2 months) diet and/or exercise regimen with or without the use of weight loss agents (including herbal medications) that has resulted in >2% weight loss. These patients may be reconsidered approximately 1 month after cessation of such intensive regimens.
- 2. Current or prior (within prior 2 months) use of any medication, including those approved to treat obesity, that could impact the efficacy results of this study (eg, orlistat, lorcaserin, phentermine-topiramate, naltrexone-bupropion, liraglutide). Patients on a stable dose and regimen (for at least 2 months) of medication to treat attention deficit hyperactivity disorder (ADHD) may be enrolled in the study as long as they agree to remain on the same dose and regimen during the study.
- 3. Prior gastric bypass surgery resulting in >10% weight loss durably maintained from the baseline preoperative weight with no evidence of weight regain. Specifically, patients may be considered if surgery was not successful, resulted in <10% weight loss compared to pre-operative baseline weight, or there is clear evidence of weight regain after an initial response to bariatric surgery. All patients with a history of bariatric surgery must be discussed with, and receive approval from, the Sponsor prior to enrollment.
- 4. Diagnosis of schizophrenia, bipolar disorder, personality disorder or other Diagnostic and Statistical Manual of Mental Disorders fifth edition (DSM-V) disorders that the Investigator believes will interfere significantly with study compliance. Neurocognitive disorders affecting ability to consent will not be disqualifying as long as an appropriate guardian able to give consent has been appointed.
- 5. In patients with no significant neurocognitive deficits:
 - A Patient Health Questionnaire-9 (PHQ-9) score of ≥15 and/or
 - Any suicidal ideation of type 4 or 5 on the C-SSRS, any lifetime history of a suicide attempt, or any suicidal behavior in the last month.
- Current, clinically significant pulmonary, cardiac, or oncologic disease considered severe enough to
 interfere with the study and/or confound the results. Any patient with a potentially clinically significant
 disease should be reviewed with the Sponsor to determine eligibility.
- 7. History of significant liver disease or liver injury, or a current liver assessment due to abnormal liver tests (as indicated by abnormal liver function tests, alanine transaminase [ALT], aspartate transaminase [AST], alkaline phosphatase, or serum bilirubin >1.5× the upper limit of normal [ULN] for any of these tests) for an etiology other than non-alcoholic fatty liver disease (NAFLD). Thus, any underlying etiology besides NAFLD, including diagnosed non-alcoholic steatohepatitis (NASH), other causes of hepatitis, or history of hepatic cirrhosis is exclusionary, but the presence of NAFLD is not be exclusionary.
- 8. Moderate to severe renal dysfunction as defined by the Cockroft Gault equation <30 mL/min. .
- 9. History or close family history (parents or siblings) of skin cancer or melanoma (excluding non-invasive basal or squamous cell lesion), or patient history of ocular-cutaneous albinism.
- 10. Significant dermatologic findings relating to melanoma or pre-melanoma skin lesions (excluding non-invasive basal or squamous cell lesion), determined as part of comprehensive skin evaluation performed by a qualified dermatologist during screening. Any concerning lesions identified during the screening period will be biopsied and results must be known to be benign prior to enrollment. If the pre-treatment biopsy results are of concern, the patient should be excluded from the study.
- 11. Patient is, in the opinion of the Study Investigator, not suitable to participate in the study.
- 12. Participation in any clinical study with an investigational drug/device within 3 months prior to the first day of dosing.
- 13. Significant hypersensitivity to study drug.
- 14. Inability to comply with the QD injection regimen.

Study Drug and Administration

All study drug (active and placebo) is for investigational use only and is to be used only within the context of this protocol. Active study drug, setmelanotide, and placebo will be supplied by the Sponsor.

Setmelanotide drug product (setmelanotide mPEG-DSPE formulation) is a sterile solution for injection. The product is manufactured at a concentration of 10.0 mg/mL.

Placebo is vehicle only and is identical in appearance to active treatment.

Setmelanotide and placebo will be administered as SC injection QD.

There will be extensive training of patients in drug administration including educational materials. Study-specific training materials will be provided to both the investigative staff and study participants and caregivers. Home nurses will be available, as needed, for additional training and to reinforce compliance. The Sponsor will provide extra placebo supplies for use during training.

Statistical Considerations

The primary statistical hypothesis is that the proportion of patients who are treated with setmelanotide for \sim 52 weeks who achieve \geq 10% reduction from baseline in body weight is greater than a historical control rate of 10% in the \geq 12 years old Full Analysis Set (\geq 12 yo FAS) (see definition in Section 8.2).

Data from the Clinical Registry Investigating Bardet-Biedl Syndrome (CRIBBS) were used to provide input for the sample size/power calculations. In particular, the natural history responder rate (percent of patients with weight loss ≥10% over a 1-year period) was assessed to determine the power estimates for the primary efficacy endpoint (see details in Section 8). The sample size is mainly driven by the primary hypothesis; although the rarity of the population is also taken into consideration.

Data from CRIBBS suggest that the proportion of subjects ≥ 12 years old who had $\geq 10\%$ spontaneous weight reduction from the previous 1-year period is approximately 6.4%. The power calculations assume a null historical control value of 10% who show at least a 10% weight loss, which is expected to be a conservative estimation. It is also expected that treatment with setmelanotide for ~ 52 weeks is associated with a true underlying probability of at least 66% who demonstrate at least 10% weight loss after ~ 52 weeks.

A sample size of 7 patients provides ~95% power at 1-sided alpha of 0.05 and ~91% power at 1-sided alpha of 0.025, to yield a statistically significant difference compared to a historical control rate of 10%, based on a one-sample test, assuming a 66% response rate in patients who are treated with setmelanotide. The Sponsor has chosen 1-sided, alpha=0.05 as the scientific success criterion associated with the primary analysis.

Although these data suggest that powering the study for the primary endpoint will require a minimal number of patients (N<10), the size of the trial is also a function of the rarity of BBS and AS and a desire to better understand the effect of setmelanotide in these patient populations. Hence, approximately 30 patients (including 6 AS patients) are planned to be enrolled in the study. This number is suitable for a single pivotal trial to support the indications in BBS and AS and to provide robust information for both the between group analysis of the placebo-controlled, double-blinded period and the one-sample comparison to the historical control response rate after the planned 38 week open-label treatment period.

The primary analysis on the primary efficacy endpoint will be based on the \geq 12 yo FAS. By nature of the study design, a small percentage of patients who are randomized into the placebo arm may have less than \sim 52 weeks of setmelanotide treatment by the timing of the primary analysis (end of Period 2); hence, a linear model based extrapolation will be used to impute their measurements after \sim 52 weeks setmelanotide treatment for the primary analysis. In general, missing values unrelated to study treatment (eg, due to lost to follow-up or missed visit) will also be imputed with the linear model based extrapolation, but missing values due to treatment-related reasons (eg, lack of efficacy or AEs) will be imputed as treatment failures. A data snapshot will be taken for the primary analysis, and a supplemental supportive analysis will be performed on a locked database following study completion.

TABLE OF CONTENTS

CLINIC	AL STUDY PROTOCOL	1
APPROV	VAL SIGNATURE PAGE	2
INVEST	IGATOR STATEMENT	3
CLINIC	AL STUDY SYNOPSIS	4
TABLE	OF CONTENTS	10
List of Ta	ables	15
List of Fi	gures	15
LIST OF	ABBREVIATIONS	16
1.	INTRODUCTION	20
1.1.	Purpose of Study	20
1.2.	Overview of Bardet Biedl and Alström Syndromes	20
1.2.1.	Bardet Biedl Syndrome	20
1.2.2.	Alström Syndrome	21

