8.5. Efficacy Analyses

8.5.1. Primary Efficacy Analysis

The primary efficacy endpoint is the proportion of patients (≥ 12 years of age at baseline) who achieve a $\geq 10\%$ reduction from baseline in body weight (ie, are 'responders') after ~ 52 weeks of treatment with setmelanotide. The statistical hypothesis for the primary efficacy endpoint is:

H0:
$$p_t \le 10\%$$
 vs H1: $p_t > 10\%$

where p_t is the response rate after \sim 52 weeks of setmelanotide treatment (ie, \sim Week 53 for patients randomized to setmelanotide and \sim Week 66 for patients randomized to placebo).

The subgroup of patients ≥12 years of age was selected for the primary analysis because this is the group of patients for whom the interpretation of weight loss is most straightforward. Normal weight gain that accompanies increases in patient height during childhood growth and development can confound interpretation of the efficacy of weight loss drugs (Kelly 2016).

The statistical hypothesis will be tested using an exact binomial test, at a 1-sided 0.05 significance level. The 1-sided 0.05 significant level was chosen based on the small sample size due to the rarity of the disease. A 2-sided 90% confidence interval (CI) will be calculated using the exact Clopper-Pearson method. The success criterion for the primary hypothesis requires the rejection of the null hypothesis at the 1-sided 0.05 significance level. The statistical criterion

corresponds to the 2-sided 90% CI for setmelanotide of the response rate excluding 10% (ie, lower bound of the CI >0.10).

The primary analysis on the primary efficacy endpoint will be based on the ≥12 yo FAS. Timing of the analysis and general missing data handling principles are described in Section 8.4. A sensitivity analysis based on data as observed (ie, no imputation on missing values) will be provided. Additional sensitivity analysis based on Per-Protocol Analysis Set will be explored as appropriate.

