1. INFORMATION FROM THE STUDY PROTOCOL

1.1. Introduction and Objectives

1.1.1. Introduction

This document presents the statistical analysis plan (SAP) for Study RM-493-023, A Phase 3 trial of Setmelanotide (RM-493), a Melanocortin-4 Receptor (MC4R) Agonist, in Bardet-Biedl Syndrome (BBS) and Alström syndrome (AS) Patients with Moderate to Severe Obesity. This SAP is based upon protocol version dated 26 August 2020.

This SAP is designed to outline the methods to be used in the analysis of study data in order to answer the study objectives. Populations for analysis, data handling rules, statistical methods, and formats for data presentation are provided. The statistical analyses and summary tabulations described in this SAP will provide the basis for the results sections of the clinical study report (CSR) for this study.

In addition, the SAP is intended to clarify many of the details of the more limited discussion in the statistical section of the protocol, therefore, the SAP will expand on and may modify the plans outlined in the study protocol. If changes are made to the plans outlined in the protocol, the SAP will supersede the relevant contents of the protocol. If, after the study has completed, changes are made to the SAP, then these deviations to the plan will be listed, along with an explanation as to why they occurred, in the Clinical Study Report for the study as appropriate. It should be noted that a cohort of the supplemental patients was added into the protocol in the midcourse of the study. However, the sponsor has specified that the patients categorized in the pivotal cohort include all the enrolled BBS/AS patients at the time of the planned sixth AS patient enrollment. Based on this definition, and up to the finalization of the SAP, it is concluded that a total of 38 patients (the first 32 BBS patients and 6 AS patients) will make up the pivotal cohort. The full list of pivotal cohort patients is provided in Appendix I. All analyses for CSR and Submission, including demographics, disposition, baseline characteristics, efficacy, and safety etc., will be performed and the conclusions will be drawn based on the data from the pivotal cohort of patients. The purpose of the supplemental cohort is to gain more treatment experience. Therefore, unless stated otherwise, all analyses in the SAP refer to pivotal cohort only.

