3. GENERAL STATISTICAL METHODS

3.2. General Methods

All data listings that contain an evaluation date will contain a relative study day (Rel Day). Pre-treatment and on-treatment study days are numbered relative to the day of the first dose of study medication which is designated as Day 1. The preceding day is Day -1, the day before that is Day -2, etc.

All output will be sorted and labeled according to the International Conference on Harmonization recommendations and formatted to the appropriate page size(s).

Tabulations will be produced for appropriate demographic, baseline, efficacy, and safety parameters. For categorical variables, summary tabulations of the number and percentage of subjects within each category of the parameter will be presented. For continuous variables, the number of subjects (N), mean, 95% confidence interval of the mean, median, standard deviation (SD), minimum, and maximum values will be presented.

Formal statistical hypothesis testing will be performed on the primary efficacy endpoint with testing conducted at the 1-sided, 2.5% level of significance. Summary statistics will be presented, as well as confidence intervals (CIs), as described in the sections below. Trial success will be based on a 1-sided p-value <0.025.

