4.3.1. Primary Efficacy Analysis

The primary efficacy analysis on the primary efficacy endpoint will be conducted in patients ≥12 years of age (at informed consent) in the FAS population.

[figure not shown]
The primary efficacy endpoint is the proportion of patients (≥ 12 years of age) who achieve a $\geq 10\%$ reduction in body weight from baseline after ~ 52 weeks of treatment. The null hypothesis (H0) to be tested is that the proportion of patients treated for ~ 52 weeks who achieve $\geq 10\%$ reduction in body weight from baseline is less than or equal to a historical control rate of 10%. The alternative hypothesis (H1) is that the proportion is greater than a historical control rate of 10%:

H0: $p_t \le 10\%$ vs H1: $p_t > 10\%$

where p_t is the response rate after ~52 weeks of treatment.

Please note that there are two different uses of "10%" above, which is explained here for clarity:

- The use of "10%" in the endpoint definition is the **response criteria** for an individual patient. If a patient achieves a ≥10% reduction from baseline in body weight, the patient will be categorized as a responder in this analysis. Otherwise, the patient will be categorized as a non-responder.
- The use of "10%" as the historical control **rate** is the historical reference/control response rate to be statistically compared to the observed response rate in patients treated with setmelanotide. The observed response **rate** of setmelanotide will be calculated with the number of responders (using the above 10% endpoint definition) divided by the number of total patients.

The primary endpoint will have binomial proportions calculated for each of the 100 imputed datasets. The outcomes from the 100 imputed datasets will be combined using Rubin's Rule to provide an overall estimate against the null hypothesis with corresponding confidence intervals and p-value (Little and Rubin, 2002). The 1-sided 0.025 significant level was chosen based on the small sample size due to the rarity of the disease. The success criterion for the primary hypothesis requires the rejection of the null hypothesis at the 1-sided 0.025 significance level. The statistical criterion corresponds to the 2-sided 95% CI for setmelanotide of the response rate excluding 10% (i.e., lower bound of the CI >0.10).

This analysis may be repeated on the following analysis sets: DUS, PP at EOP2, SH, AG, as appropriate.

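### The synopsis states ~91% power for 7 patients at one-sided 0.025; the exact binomial test named in Protocol 8.5.1 gives 81.6%

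*Protocol*

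**What the plan says.** The power statement is in the protocol synopsis under Statistical Considerations: "A sample size of 7 patients provides ~95% power at 1-sided alpha of 0.05 and ~91% power at 1-sided alpha of 0.025". Its inputs are given there too: "The power calculations assume a null historical control value of 10% who show at least a 10% weight loss", and "assuming a 66% response rate in patients who are treated with setmelanotide". The synopsis attributes the result to a one-sample test without saying which, and concludes that "powering the study for the primary endpoint will require a minimal number of patients (N<10"). It then plans about 30 patients because the diseases are rare and more experience is wanted.

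Protocol 8.5.1 names the primary test: "The statistical hypothesis will be tested using an exact binomial test, at a 1-sided 0.05". It pairs this with a two-sided 90% Clopper-Pearson interval whose lower bound must exceed 10%.

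The SAP sets a stricter level. Section 3.2 says: "Trial success will be based on a 1-sided p-value <0.025". Section 4.3.1 describes the primary analysis as responder proportions from multiply imputed data: "The outcomes from the 100 imputed datasets will be combined using Rubin's Rule to provide an overall estimate against the null hypothesis". Its public text names neither an exact test nor a standard error. SAP 1.1.1 gives the actual size: "a total of 38 patients (the first 32 BBS patients and 6 AS patients) will make up the pivotal cohort".

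**The concern.** A one-sample test on 7 patients with a binary outcome can only reject at a whole number of responders, so only a few power values are possible. The drop from ~95% to ~91% when alpha is halved is smoother than such a test allows at this size. It suggests a continuous approximation placed beside an exact test.

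The consequence is limited to how the plan reads. The synopsis holds the only public power statement, and its 0.025 figure is the one at the SAP's success level. A reader would take ~91% as the chance of success with 7 patients. Under the exact test the chance of missing success is 18.4% (100 − 81.6), about twice the 9% implied.

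**Working it through.** **Inputs.** n = 7, null rate p0 = 0.10, assumed response p1 = 0.66, one-sided alpha 0.05 and 0.025 (synopsis). Exact binomial test (Protocol 8.5.1). Success at one-sided 0.025 (SAP 3.2 and 4.3.1).

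**1. Reproducing the stated figures.** The one-sample arcsine approximation is power = Φ(h√n − z), with h = 2·asin(√0.66) − 2·asin(√0.10) = 1.2530 and h√7 = 3.315.

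- At 0.05: Φ(3.315 − 1.645) = 95.3%
- At 0.025: Φ(3.315 − 1.960) = 91.2%

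Both match. Of the other approximations tried, none comes within 2 points of the stated figure at both levels:

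| Approximation | Power at 0.05 | Power at 0.025 |
|---|---|---|
| Normal, null and alternative variances | 98.2% | 97.0% |
| Same, with continuity correction | 95.4% | 93.2% |
| Normal, alternative variance only | 93.1% | 87.9% |
| Normal, null variance only | 99.95% | 99.9% |
| Arcsine with continuity correction | 90.0% | 83.3% |
| Noncentral t | 86.6% | 74.1% |

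**2. What 7 patients can give.** X is the number of responders.

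| Reject if X is at least | Actual alpha, X ~ Bin(7, 0.10) | Power, X ~ Bin(7, 0.66) |
|---|---|---|
| 2 | 0.1497 | 99.2% |
| 3 | 0.0257 | 95.1% |
| 4 | 0.0027 | 81.6% |
| 5 | 0.0002 | 55.5% |

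No row is near 91%.

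**3. The exact test at each level.**

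- At 0.05: 0.0257 ≤ 0.05, so 3 of 7 is enough and power is 95.1%. The stated ~95% is correct.
- At 0.025: 0.0257 > 0.025, so 4 of 7 is needed and power is 81.6%. The difference from the stated figure is 91 − 81.6 = 9.4 points.

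The Clopper-Pearson 95% lower bound agrees: 0.099 for 3/7, which does not exclude 10%, and 0.184 for 4/7, which does.

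**4. Rounding of the 66%.** Power with a cut-off of 4 is 80.8% at p1 = 0.655, 82.4% at 0.665 and 82.7% at 2/3. Rounding does not explain the gap.

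**5. The SAP's pooled analysis.** The SAP gives no standard error, so two common choices are shown, assuming no imputed values.

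- Wald 95% lower bound: 0.062 for 3/7 and 0.205 for 4/7. It needs 4 of 7, so power is 81.6%.
- Null-variance z at 3/7: (0.4286 − 0.10)/√(0.09/7) = 2.90. It rejects at 3 of 7, so power is 95.1%, with actual alpha 0.0257.

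Neither gives 91%.

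**6. Other sample sizes, exact test at one-sided 0.025.**

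| n | Cut-off | Power |
|---|---|---|
| 6 | 3 | 89.3% |
| 7 | 4 | 81.6% |
| 8 | 4 | 90.5% |
| 9 | 4 | 95.3% |
| 20 | 6 | 99.98% |
| 30 | 8 | >99.99% |
| 38 | 9 | >99.99% |

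**The case against.** The strongest objection is that 81.6% belongs to a combination no public text plans. Protocol 8.5.1 pairs the exact test with 0.05, the protocol's chosen criterion, and there the stated power is right. The SAP, which takes precedence, uses 0.025 but pools proportions with Rubin's rules and names no exact test. Depending on the standard error, its power at n = 7 could be 81.6% or 95.1%, and 91% lies between them. This is correct as far as it goes. It does not rescue the stated figure, because lying between two attainable values is not the same as being attainable. The synopsis itself quotes power at 0.025, and the exact test is the only one-sample test the protocol names for this endpoint.

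Second, the detailed sample-size text (Protocol 8.1) is not public and may name the method. That stands: the use of an arcsine formula is inferred from the numerical match, and nothing here claims that the method is unnamed in the full plan. Naming it would explain ~91% but would not make it the power of the exact test.

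Third, n = 7 is a low point caused by discreteness. The cut-off of 3 misses 0.025 by only 0.0007, and n = 6 and n = 8 give about 90%. An approximation marked as such describes that neighbourhood fairly. This also stands as an explanation, but the sentence makes a claim about 7 patients specifically.

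Fourth, nothing depends on the figure. That stands in full and sets the grade.

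**Conclusion.** The concern holds, as a minor point. For 7 patients, a 10% null rate and a 66% response rate, the power at one-sided 0.025 is 81.6% under the exact binomial test, about 9 points below the ~91% stated. The ~95% at 0.05 is correct.

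The conclusion assumes complete data with no imputed outcomes; the synopsis power statement mentions none. That no cut-off gives about 91% does not depend on which one-sample test is chosen, nor on the arcsine explanation.

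The trial's actual power is not in doubt. The documents do not give the number aged 12 or over. Assuming 20 to 38, exact power at 0.025 is above 99.9%. The conclusion that fewer than 10 patients would be enough also stands, since 8 give 90.5% and 9 give 95.3%. No decision, enrolment target or conclusion changes.

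**What to change.** Replace the power sentence in the synopsis, and any matching sentence in the sample-size section, with wording to this effect:

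> With the exact binomial test, 7 patients give ~95% power at one-sided 0.05 and ~82% at one-sided 0.025; 8 patients give ~91% at one-sided 0.025.

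This names the test and makes each figure reproducible from the stated 10% and 66%. The cost is a text correction in which one figure becomes less favourable. Enrolment and the analysis are unaffected.
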